Study objectives and endpoints for Part A were updated; primary endpoint will assess RSA as the average of both arms instead of dominant arm only and an exploratory endpoint was added to assess RSA in dominant or non-dominant arms separately. This change was made to provide a more robust assessment of shoulder mobility. Shoulder strength assessed by hand-held quantitative dynamometry was changed from an exploratory to a secondary endpoint. Statistical analyses were updated as appropriate.	Synopsis , Section 2.1 , Section 9.1
Oral CYP3A4, OAT3, and MATE substrates are no longer systematically prohibited as concomitant medications. This change is based on the results of the recently completed drug-drug interaction study (1821-CLP-102). Only those concomitant medications that are substrates of OAT1/OAT3 and have a narrow therapeutic index may need to have their blood levels monitored when coadministered with losmapimod. The following changes were made: 
Background sections were updated (Section 1.3.4)Exclusion criteria were updated for Part A (EC #3 and #4) and for Part B (EC #2) (Section 4.1)Concomitant medications were updated (Section 5.8)Contraception guidelines were updated; oral combined	Section 1.3.4 , Section 4.1 , Section 5.5 , Section 5.5.1 , Section 5.8 , Appendix 4

Change and Rationale	Affected Sections

hormonal methods are now allowed (Section 5.5.1).
 
 • List of CYP3A4, OAT1, and OAT3 substrates in Appendix 3 was deleted and a list of OAT1/OAT3 substrates with narrow therapeutic index (NTI) was added as a new Appendix 4. • Lifestyle restrictions were updated; subjects no longer have to avoid nutrients known to modulate CYP enzyme activity (Section 5.5). 	

Clarified the study duration of Part B (OLE). The OLE will last for approximately 2 years, according to the visits defined in the OLE schedule of assessments (Table 8). Any plans to extend the study duration will be executed in a future amendment. The phrase “until after commercial drug is available post regulatory approval” was also deleted.
	
Synopsis, Section 3.1, Section 3.1.2, Appendix 1

Added clarification for safety follow-up visits for clarity; only subjects that do not continue to the OLE will complete the safety follow-up visits in Part A.
	
Synopsis, Section 3.1.1, Appendix 1

IDMC	Independent Data Monitoring Committee
IEC	Independent Ethics Committee
Ig	immunoglobulin
IPC	investigational product complaint
IRB	Institutional Review Board
IRT	interactive response technology
KLH	keyhole limpet hemocyanin
LME	linear mixed-effects model
LMV	lean muscle volume
LS	least squares
MAPK	mitogen-activated protein kinase
MATE	multidrug and toxin extrusion
MedDRA	Medical Dictionary for Regulatory Activities
MFF	muscle fat fraction
MFI	muscle fat infiltration
MMRM	mixed-effects model for repeated measures
MRI	magnetic resonance imaging
Neuro-QoL	Quality of Life in Neurologic Disorders
[REDACTED]	[REDACTED]
OAT	organic anion transporter
OLE	open-label extension
OLS	open-label study
PD	pharmacodynamic(s)
PGIC	Patient Global Impression of Change
[REDACTED]	[REDACTED]
pHSP27	phosphorylated heat shock protein 27
PI	Principle Investigator
PK	pharmacokinetic(s)
PO	orally
PRO	patient-reported outcome
PVG	pharmacovigilance
Q	quintant/quadrant

Abbreviation	Definition
QTc	QT interval corrected
QTcF	QT interval corrected for heart rate by Fridericia's formula
RSA	relative surface area
RWS	reachable workspace
SAE	serious adverse event
SAP	statistical analysis plan
SMCHD1	structural maintenance of chromosomes flexible hinge domain 1
SRC	Safety Review Committee
SUSAR	suspected unexpected serious adverse reaction
TDAR	T-cell-dependent antibody response
TEAE	treatment-emergent adverse event
UE	upper extremity
ULN	upper limit of normal
WB	whole-body

PROTOCOL SYNOPSIS

Protocol Number:	1821-FSH-301
Title:	A Phase 3 Global, Randomized, Double-Blind, Placebo-Controlled, 48-Week, Parallel-Group Study of the Efficacy and Safety of Losmapimod in Treating Patients with Facioscapulohumeral Muscular Dystrophy (FSHD) (REACH)
Sponsor:	Fulcrum Therapeutics, Inc. [name]
Study Phase:	3
Study Sites:	Approximately 36 sites in North America and Europe
Indication:	FSHD
Rationale:	Treatment of FSHD with losmapimod has demonstrated evidence of slowing of disease progression and/or improvement on clinical outcome assessments in people living with FSHD. Nonclinical studies have shown that losmapimod reduces the aberrant expression of double homeobox 4 (DUX4); the underlying cause of FSHD. Two Phase 2 clinical studies, a 48-week randomized controlled study (ReDUX4, FIS-002-2019) and a 52-week open-label study (OLS, FIS-001-2019) demonstrate evidence of benefit of treatment with losmapimod on structural and FSHD-relevant clinical endpoints that is recognized by patients, and a favorable safety and tolerability profile supporting continued development.
Objectives:	
Part A: Placebo-Controlled Treatment Period
 
Primary Objective:
 
• To evaluate the efficacy of losmapimod for the treatment of FSHD on disease progression assessed by reachable workspace quantification of total relative surface area (RSA) Q1-Q5 with 500 g wrist weight, averaged over both arms 
Secondary Objectives:
 
• To evaluate Patient Global Impression of Change (PGIC) relative to placebo• To evaluate efficacy of losmapimod to slow accumulation of fat in muscle-by-muscle fat infiltration (MFI) with whole-body (WB) musculoskeletal (MSK) magnetic resonance imaging (MRI) relative to placebo• To evaluate relative change from baseline in shoulder strength by hand-held quantitative dynamometry relative to placebo• To evaluate the change in Quality of Life in Neurological Disorders: Upper Extremities (Neuro-QoL UE) relative to placebo

	
• To assess safety and tolerability of losmapimod in patients with FSHD 
Exploratory Objectives:
  
• To evaluate relative change from baseline in muscle strength by handheld quantitative dynamometry, relative to placebo  
Part B: Open-Label Extension
 
Primary Objective:
 
• To assess the long-term safety and tolerability of losmapimod in patients with FSHD 
Exploratory Objectives:
 
Endpoints:	
Part A: Placebo-Controlled Treatment Period
 
Primary Endpoints:
 
• Change from baseline in average total RSA Q1--Q5 with 500 g wrist weight at Week 48, where average is applied over both arms 
Secondary Endpoints:
 
• PGIC at Week 48• Change from baseline in WB longitudinal composite MFI of B muscles

at Week 48

[figure not shown]
- Relative change from baseline in average shoulder abductor strength by hand-held quantitative dynamometry at Week 48
- Change from baseline in Neuro-QoL UE at Week 48
- Safety and tolerability, based on the assessment of adverse events (AEs), clinical laboratory tests, electrocardiograms (ECGs), vital signs, and physical examinations

Exploratory Endpoints:

- Change from baseline in WB longitudinal composite MFF at Week 48

- Relative change from baseline in muscle strength by hand-held quantitative dynamometry at Week 48

[figure not shown]

Part B: Open-Label Extension

Primary Endpoint:

- Safety and tolerability of long-term treatment with losmapimod, based on the assessment of AEs, clinical laboratory tests, ECGs, vital signs, and physical examinations

Exploratory Endpoints:

	
 • [REDACTED]
Study Population:	
Part A: Males and females between the ages of 18 to 65 years, inclusive, with a diagnosis of FSHD1 or FSHD2 verified by genetic testing and a Clinical Severity Score of 2 to 4 (Ricci score; range 0 to 5), with no contraindications to MRI.
 
Part B: Patients who have completed Part A of this study.

Study Design:	
Part A of Study 1821-FSH-301 is a global, randomized, double-blind, placebo-controlled, parallel-group, multicenter study. Efficacy and safety of losmapimod will be evaluated in patients with FSHD over a 48-week treatment period. A total of approximately 230 patients with FSHD will be randomized 1:1 to receive losmapimod or placebo.
 
Upon completion of Part A, patients will have the option to rollover into Part B, the open-label extension. The long-term safety, tolerability, and efficacy of losmapimod will be evaluated in patients.

Duration of Treatment:	
Part A: Placebo-Controlled Treatment Period
 
Patients will participate in the randomized, controlled treatment period, including the following:
 
 • [REDACTED] • A 48-week placebo-controlled treatment period. • Safety follow-up visits [REDACTED] days and [REDACTED] days after last dose (only for patients who discontinue from treatment early or who do not rollover into Part B). 
 – For patients who rollover into Part B, the Week 48 visit will be the end of study visit for Part A. • Patients will have the opportunity to rollover into Part B (open-label extension) after completing Part A. Approval from the Medical Monitor will be required if patients do not rollover without interruption after completing the Week 48 assessments. If a patient rolls over more than 7 days after the last dose in Part A, they may be required to repeat selected Week 48 assessments at the discretion of the Medical Monitor. 
Part B: Open-Label Extension
 
 • Patients may participate in the open-label extension after completing Part A. • All patients in Part B will be eligible to receive losmapimod 15 mg orally twice daily (BID) from the time they complete Part A of this study and for the duration of the study as specified in the Schedule of Assessments for Part B or until the study is discontinued by the sponsor. • Patients will have safety follow-up visits [REDACTED] and [REDACTED] days after the last dose.
Details of Applicable Monitoring	In Part A only, an Independent Data Monitoring Committee (IDMC) will conduct periodic planned safety reviews of study data, as outlined in the IDMC

Committee:	charter.
Investigational Product, Dosage, and Route of Administration:	
Part A: Placebo-Controlled Treatment Period Losmapimod 15 mg will be administered orally BID with food. Placebo tablets (Part A only) will be identical in appearance to losmapimod tablets and will have the same excipients as the active tablets.
 
Part B: Open-Label Extension Losmapimod 15 mg will be administered orally BID with food for the duration of the study as specified in the Schedule of Assessments for Part B or until the study is discontinued by the sponsor.

Sample Size:	
Part A: Placebo-Controlled Treatment Period Approximately 210 patients with genetically confirmed FSHD1 and 20 patients with genetically confirmed FSHD2 will be enrolled. All previous FSHD studies of losmapimod have been conducted in patients with FSHD1; therefore, sample size calculations are based on patients with FSHD1 genotype. Additional patients with FSHD2 genotype will be enrolled to explore safety and efficacy in this subgroup. Assuming the within-group SD of change is 0.08 and that 10% of the study population has missing Week 48 data, a sample size of 210 patients with FSHD1 (105 patients per group) will be needed to provide at least 95% power with a 2-sided test at 0.05 significance level to detect a difference of 0.05 between losmapimod and placebo in change from baseline in average total RSA Q1-Q5 with 500 g wrist weight at Week 48. An additional approximately 20 patients with FSHD2 will be recruited.
 
Part B: Open-Label Extension Patients who complete Part A will be given the opportunity to participate in Part B. The sample size is not based on any formal statistical assumptions. Up to 230 patients may be enrolled in Part B.

Statistical Methods:	
Part A: Placebo-Controlled Treatment Period The primary endpoint of absolute change from baseline in average total RSA Q1-Q5 with 500 g wrist weight at Week 48 will be formally tested only during the final analysis, when all patients complete Part A participation. The full analysis set (FAS) will be used for the primary analysis in the placebo-controlled treatment period. The FAS will consist of all patients with FSHD1 and FSHD2 who are randomized and receive at least 1 dose of study drug in the placebo-controlled treatment period. The analysis of the absolute change from baseline in average total RSA will be based on a mixed-effects model for repeated measures with the absolute change from baseline at post-baseline visits up to Week 48 as the dependent variable. The model will include terms for treatment group, visit, treatment group by visit interaction, baseline value, baseline value by visit interaction, region, and FSHD repeat number category, where appropriate. An unstructured covariance matrix will be used to model the correlations between repeated measurements within each patient. The Kenward-Roger approximation will be used to estimate the denominator degrees of freedom.
 
Part B: Open-Label Extension The open-label analysis set will be used for all analyses, unless otherwise

	specified, for Part B. It will consist of all patients who receive at least 1 dose of losmapimod in the open-label extension portion. All statistical analyses will be descriptive. The statistical methods are described in Section 9.2.5 and in the Statistical Analysis Plan.
Version and Date of Protocol	Version 5.1, 21 December 2023

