The natural history of FSHD disease progression has been captured in a longitudinal assessment of reachable workspace (RWS). Total relative surface area (RSA) quadrants (Q1-Q4) demonstrates an annualized 1.63% RSA decline over 5 years across patients with FSHD assessed without weights and a significant 1.82% RSA decline in total RWS with weights ([Hatch, Kim, et al. 2019](#)). Moderately impaired individuals with baseline RSA values between 0.20 and 0.70 (out of 1.0, for quadrants Q1-Q4) were more likely to show predictable declines over time with an annualized total RSA loss of 2.74% ($P=0.047$) ([Hatch, Kim, et al. 2019](#)).

Muscle strength, measured by quantitative muscle testing, decreases at a rate of approximately 1% to 4% per year ([Statland and Tawil 2014](#); [Stübgen and Stipp 2010](#)), and a 6-year risk of wheelchair use is 24% ([Statland, Shah, et al. 2015](#)). Asymmetry of muscle involvement is common. In the most severe cases, there can be extramuscular manifestations, including retinal vascular changes and hearing loss ([Statland and Tawil 2014](#)); cardiac and respiratory muscles are usually spared.

FSHD is caused by aberrant expression of the DUX4 gene, a homeobox transcription factor. DUX4 pathological expression in skeletal muscle in both FSHD type 1 (FSHD1) and FSHD type 2 (FSHD2) leads to the activation of genes usually not expressed in skeletal muscle and almost exclusively found in the early embryo (Bosnakovski et al. 2014; Homma et al. 2015; Jagannathan et al. 2016; Yao et al. 2014). This aberrant *DUX4*-driven gene expression activates complex pathological cell processes including expression of cytokines (Statland, Odrzywolski, et al. 2015), cellular stress, and programmed cell death (apoptosis) with no single process currently defined as driving the pathology (Wang et al. 2019; Wong et al. 2020). The result is myofiber death with skeletal muscle tissue loss, as well as muscle fat infiltration and eventual replacement by fat. This loss of muscle tissue and replacement by fat is responsible for the clinical manifestation of the disease, including progressive loss of muscle strength and strength (muscle weakness), loss of function, and slow accumulation of physical disability.

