9.1.6.4. Analysis of Secondary Efficacy Endpoints

Secondary endpoints (detailed in [Section 2.1.2](#)) will be summarized using descriptive statistics.

Continuous endpoints with multiple post-baseline assessments will be analyzed using an MMRM model analogous to the one used for the primary analysis of the primary endpoint based on the FAS. They will also be analyzed using an LME model analogous to the linear trend analysis in [Section 9.1.6.3](#) based on the FAS, where appropriate. Relative changes from baseline will be analyzed using the Wilcoxon rank-sum test, stratified by the FSHD repeat number category. The Hodges-Lehmann estimate of the associated treatment difference and asymptotic nonparametric

95% confidence interval will be computed. For all patients, changes in measurements will be calculated relative to measurements obtained at baseline.

Further details of these endpoints and analyses are presented in [Section 2.1.2](#) and the SAP for Part A.

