5. SAMPLE SIZE CONSIDERATIONS

The target population for this clinical trial is patients with FSHD1 and FSHD2. The clinical trial will reflect the current epidemiologic information about FSHD, with patients with FSHD1 making up approximately 95% of the study population and the other 5% being people living with FSHD2.

Assuming the within-group standard deviation (SD) of change is 0.08, a sample size of 210 patients with FSHD1 (105 patients per group) will be needed to provide at least 95% power with a 2-sided t-test at 0.05 significance level to detect a difference of 0.05 between losmapimod and placebo for the primary endpoint. An additional approximately 20 patients with FSHD2 will be recruited. The primary analysis will include patients with FSHD1 and FSHD2. Premature withdrawal and missing data are discussed in 9.1.

For the secondary efficacy endpoints of change from baseline in WB longitudinal composite MFI of B Muscles and PGIC at Week 48, assuming the within-group SDs are 0.72 and 1.0 respectively, a sample size of 210 patients with FSHD1 will provide at least 95% power with a 2-sided t-test at 0.025 significance level to detect a difference of 0.5 and 0.6 respectively between losmapimod and placebo.

For the secondary efficacy endpoint of relative change from baseline in average shoulder abductor strength at Week 48, assuming the within-group SD is 46, a sample size of 210 patients with FSHD1 will provide at least 75% power with a 2-sided Wilcoxon rank-sum test at 0.025 significance level to detect a difference of 20.2 between losmapimod and placebo.

In the above calculations, the assumed treatment differences and SDs are based on results from an ongoing Phase 2 study, Study FIS-002-2019 (ReDUX4). It is also assumed that 10% of the study population has missing Week 48 data. All power calculations were performed using the POWER Procedure of SAS[®] Version 9.4.

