9.2 BASELINE AND CHANGE FROM BASELINE

For all endpoints, the baseline value is defined as the last non-missing value obtained prior to the first dose of study treatment.

For continuous laboratory variables, electrocardiogram (ECG) data and vital signs, if two visits are equally eligible to assess patient status at baseline (e.g., screening and baseline assessments both on the same date prior to first dose with no washout or other intervention in the screening period), the average will be used as the baseline value. In the scenario where there are two assessments on day 1, one with time recorded and the other without time recorded, the one with time recorded will be selected as baseline. Where safety data will be summarized over time, time on study will be calculated in relation to date of first study treatment.

In all summaries, change from baseline variables will be calculated as the post-treatment value minus the value at baseline. The percentage change (relative change) from baseline will be calculated as:

$$100 \times (\text{Post-baseline value} - \text{Baseline value}) / (\text{Baseline value})$$

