This sensitivity analysis of the primary endpoint will evaluate the robustness of the primary analysis of the primary endpoint against model assumptions of normal residuals and linear relationship between the response and covariates. The rank two-way repeated measures ANCOVA will be applied upon rank transformed response and rank transformed covariates. Here, the response is change from baseline in average total RSA Q1-Q5 with 500 g wrist weight, the two factors are treatment group and visit, and the covariates are baseline value of average total RSA Q1-Q5 with 500 g wrist weight, baseline value by visit interaction, stratification category, and region. Ranks are applied at each visit within the FAS, not within each treatment group. The generalized estimating equation technique will be employed to construct rank tests [7].

Sensitivity Analysis 6: MMRM adjusting for correct FSHD repeat number category

This sensitivity analysis of the primary endpoint will be similar to that used for the primary analysis of the primary endpoint. The key difference is that, for patients with stratification category used at randomization being different from the correct category, this MMRM will adjust for the correct category.

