10.2.2.2 Change from baseline in whole body (WB) longitudinal composite MFI (B muscles)

This endpoint will follow the same method of analysis as for the primary endpoint (see 10.2.1.1) using an MMRM. The primary analysis of this endpoint will be based on the MMRM. An LME will also be fitted as defined in 10.2.1.1, where the dependent variable is absolute WB composite MFI, measured at baseline and each post-baseline visit.

Additionally, this endpoint will be analyzed using the Wilcoxon rank-sum test, stratified by the FSHD repeat number category (see 8.2). The Hodges-Lehmann estimate of the associated treatment

REACH TRIAL

difference and asymptotic nonparametric 95% confidence interval will be computed. Median change from baseline will be plotted by treatment group.

A sensitivity analysis of this endpoint will be carried out based on the on-treatment measurements up to 2 days (inclusive) after the last dose of study drug for patients in the FAS. Another sensitivity analysis will adjust for correct FSHD repeat number category (see 10.2.1.2).

The analysis will be repeated for each subgroup listed in Section 8.5.

All WB longitudinal composite endpoint data and cross-sectional composite data (MFI/MFF/LMV) will be presented by patient in a listing, by FSHD type and treatment group.

10.2.2.3 Relative change from baseline in average shoulder abductor strength by handheld quantitative dynamometry at Week 48

This endpoint will be analyzed using the Wilcoxon rank-sum test, stratified by the randomization stratification factor (see 8.2). The Hodges-Lehmann estimate of the associated treatment difference and asymptotic nonparametric 95% confidence interval will be computed. Median relative change from baseline will be plotted by treatment group.

A sensitivity analysis of this endpoint will be carried out based on the on-treatment measurements up to 2 days (inclusive) after the last dose of study drug for patients in the FAS. Another sensitivity analysis will adjust for correct FSHD repeat number category (see 10.2.1.2).

The analysis will be repeated for each subgroup listed in Section 8.5.

All dynamometry data will be presented by patient in a listing, by FSHD type and treatment group.

[figure not shown]

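### Shoulder strength is the only alpha-protected change endpoint tested without adjustment for its baseline, and it has the lowest stated power; a rank test adjusted for baseline could recover a modest amount

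*Protocol*

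**What the plan says.** The protocol (Synopsis and Section 2.1.2) and SAP 2.3.2 list as a secondary endpoint "Relative change from baseline in average shoulder abductor strength by hand-held quantitative dynamometry at Week 48". SAP 9.2 defines relative change as 100 × (post-baseline − baseline)/baseline. It also states that "the baseline value is defined as the last non-missing value obtained prior to the first dose of study treatment". The schedule of assessments places dynamometry at the baseline visit but not at screening, so the divisor comes from one visit. SAP 9.3.3.2 adds that strength is measured three times on each arm, and that the two arm means are averaged.

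Protocol 9.1.6.4: "Relative changes from baseline will be analyzed using the Wilcoxon rank-sum test, stratified by the FSHD repeat number category". SAP 10.2.2.3: "This endpoint will be analyzed using the Wilcoxon rank-sum test, stratified by the randomization stratification factor". The two sensitivity analyses for this endpoint (on-treatment data; correct repeat category) add no baseline term.

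RSA, MFI and Neuro-QoL-UE are tested by MMRM with baseline and baseline-by-visit terms (SAP 8.3.1, 10.2.1.1, 10.2.2.2, 10.2.2.4). PGIC has no baseline value.

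On power, SAP 5 says "assuming the within-group SD is 46, a sample size of 210 patients with FSHD1 will provide at least 75% power" to detect a difference of 20.2 at two-sided 0.025. The primary endpoint, MFI and PGIC are each given at least 95%. No power is stated for Neuro-QoL-UE.

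**The concern.** Any error in the baseline reading enters the outcome through the divisor. A chance-high baseline pulls the relative change down, and a chance-low one pushes it up. Some negative correlation between baseline and relative change is therefore expected. A Wilcoxon test stratified only by repeat category leaves that variation in the comparison. It also leaves in any chance difference in baseline strength between the arms.

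Under SAP 2.4.2, strength shares step 2 with MFI at 0.025 each. If both succeed, 0.05 passes to PGIC and then to Neuro-QoL-UE; if only one succeeds, 0.025 passes. At stake are the chance of success on strength itself and the alpha left for the two patient-reported endpoints.

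**Working it through.** **Inputs from SAP 5.** Difference 20.2; SD 46; two-sided alpha 0.025 (z = 2.241); 105 FSHD1 patients per group; 10% missing at Week 48, which leaves 94.5 per group.

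**The plan's own figure.** Normal approximation with Wilcoxon efficiency 3/π:
- Effective n = 94.5 × 3/π = 90.2 per group.
- 20.2 / (46 × √(2/90.2)) = 2.950.
- Power = Φ(2.950 − 2.241) = 76.1%.

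Noether's formula gives 74.6%. Simulated Wilcoxon tests on normal data give 75.0% (94 per group) and 75.6% (95 per group). The stated 75% reproduces.

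**The full analysis set.** The test will be run on FSHD1 and FSHD2 together: 230 × 0.9 / 2 = 103.5 per group. If FSHD2 patients share the assumed effect and SD, effective n is 98.8, the ratio is 3.087, and power is Φ(3.087 − 2.241) = 80.1%.

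**Effect of adjusting for baseline (FSHD1 basis, 94.5 per group).** The residual SD is 46 × √(1 − ρ²), where ρ is the within-group correlation of baseline with outcome. The documents give no ρ, so these values are assumptions.

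| Size of ρ | Power |
|---|---|
| 0 | 76.1% |
| 0.1 | 76.5% |
| 0.2 | 77.9% |
| 0.3 | 80.3% |
| 0.4 | 83.6% |

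If measurement error is the only source of correlation, then in size ρ = √((1 − R)/2), where R is the reliability of a single-visit value. The simulation columns compare a plain Wilcoxon test with ranks adjusted for baseline rank. They use 94 per group, no strata, multiplicative error, 90% of the log-ratio variance as error, and 4,000 replicates.

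| Assumed R | Size of ρ | Power by formula | Simulated Wilcoxon | Simulated adjusted |
|---|---|---|---|---|
| 0.95 | 0.158 | 77.2% | 74.7% | 75.6% |
| 0.90 | 0.224 | 78.4% | 75.8% | 77.0% |
| 0.80 | 0.316 | 80.7% | 74.8% | 79.0% |
| 0.70 | 0.387 | 83.1% | 75.4% | 81.1% |

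The gain is about 1 to 7 points by formula and about 1 to 6 by simulation.

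A second simulation used three strata (assumed 25/66/9%) and treated all change as visit error. For an assumed between-patient log-SD of 0.4, 0.6 and 0.8, power rose from 76% to 82%, 77% to 80%, and 76% to 78%. With only half the variance as error, the gain was 0 to 2 points. Across the simulations, null rejection was about 1.9% to 3.1% for both tests, against a nominal 2.5%.

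**Chance imbalance.** The SE of the baseline difference is √(2/94) = 0.146 SD, so a difference beyond 0.2 SD has probability about 0.17. With ρ of 0.3 to 0.4 in size, 0.2 SD moves the unadjusted estimate by 0.3 × 0.2 × 46 = 2.8 to 0.4 × 0.2 × 46 = 3.7 points, against the assumed 20.2.

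**The gate.** MFI: 0.5 / (0.72 × √(2/94.5)) = 4.77, so power is Φ(4.77 − 2.241) = 99.4%. Treating the two tests as independent, the chance that at least one succeeds is 1 − 0.006 × 0.239 = 99.9%. With strength power at 82% it is still 99.9%. The chance that both succeed, which passes on the full 0.05, is 0.994 × 0.761 = 76% against 0.994 × 0.82 = 82%.

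**The case against.** The strongest reply is that the planned test is valid, prespecified and simple, and that the gain is small and cannot be computed from the documents. That stands. A reader might infer more than the documents support in five ways.

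- **That most of the SD of 46 must be noise.** Protocol Section 1 says "Muscle strength, measured by quantitative muscle testing, decreases at a rate of approximately 1% to 4% per year". This is an average rate and does not bound the spread of true change between patients. The assumed treatment difference of 20.2 is itself several times that rate.
- **That the baseline is one noisy reading.** It comes from one visit, but it averages three readings on each of two arms. In the all-error simulation, the 6-point gain implies a reliability of about 0.66 for that average. The 3- and 2-point gains imply about 0.81 and 0.89.
- **That the test is biased or inflates error.** Chance imbalance can fall either way and is already covered by the test's error rate. The simulations show no difference in type I error.
- **That access to PGIC and Neuro-QoL-UE hangs on strength.** Either step-2 success opens the gate, and MFI has about 99% power on the stated assumptions. PGIC already has at least 95% stated power at 0.025.
- **That omitting region breaches SAP 8.2.** That rule concerns fixed effects in inferential models. A rank-sum test has none, and SAP 10.2.2.3 is the specific rule.

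The plan also partly covers the point. SAP 10.2.3.11 analyses absolute change in average shoulder abductor strength by the primary endpoint's baseline-adjusted method. That analysis is exploratory and has a different estimand, so it cannot stand in for the protected test.

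**Conclusion.** The point holds as a modest efficiency gain and does not invalidate the planned test. Strength is the only alpha-protected change-from-baseline endpoint tested without its baseline, and it has the lowest stated power: at least 75% for the 210 FSHD1 patients, or about 80% on the full analysis set if FSHD2 patients share the assumed effect and SD.

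The direction of the gain follows from the way the endpoint is built. Its size rests on an assumed reliability or baseline correlation: about 0 to 6 or 7 points, and near 1 or 2 if reliability is 0.90 or better. No simulated setting showed a loss beyond simulation error. The practical return is a somewhat better chance on this endpoint and of passing on 0.05 instead of 0.025.

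**What to change.** Before unblinding, change SAP 10.2.2.3 so that the alpha-protected p-value comes from a stratified rank ANCOVA:

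1. Within each randomization stratum, rank the Week 48 relative change and the baseline average strength.
2. Regress the first ranks on the second.
3. Apply the van Elteren test to the residuals.

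Keep the unadjusted stratified Wilcoxon test as a sensitivity analysis. Keep the Hodges-Lehmann estimate, and report a baseline-adjusted treatment estimate beside it, because the unadjusted Hodges-Lehmann estimate does not correct chance baseline imbalance.

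Align protocol 9.1.6.4, or record the departure in SAP 11, which now lists no changes from the protocol. The SAP has a precedent in the primary endpoint's fifth sensitivity analysis: "The rank two-way repeated measures ANCOVA will be applied upon rank transformed response and rank transformed covariates".

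The cost is a few lines of text and programming. No patient is lost, because anyone with a Week 48 relative change has a baseline value. The endpoint stays the same. The small downside is that the Hodges-Lehmann interval will no longer match the p-value exactly.
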